## 8.3.5 Sensitivity Analyses of the Co-Primary Efficacy Endpoints

As stated in Section 8.2.1.1, multiple imputations procedures for missing HDSM-Ax-7 and GSP values will be performed prior to the co-primary efficacy analyses under MAR and MNAR assumptions. In order to support the results of the co-primary GSP analysis, the ranked GSP and non-rank-transformed GSP ANCOVA analyses will be repeated without imputing missing data, and again after removing outlier data. To further explore the robustness of the primary analysis results to different missing data assumptions, analyses using two additional imputation methods will be performed as presented below. The first is an analysis of the HDSM-AX-7 co-primary endpoint with missing data imputed as failure/non-response. The second is a tipping point analysis on both co-primary endpoints, using multiple imputations for missing data. Additionally, the 7 items in the HDSM-Ax-7 scale will be analyzed individually to support the primary analysis for this co-primary endpoint. The below sensitivity analyses will be performed using the ITT Population and the mITT Population.

Table 8-2 Summary of Sensitivity Analyses of the Co-Primary Efficacy Endpoints

Sensitivity Analysis Number	Co-Primary Efficacy Outcome Assessed	Sensitivity Analysis	Populations
1	GSP change from baseline to EOT	Analysis performed on available data only without imputing missing data; using both ranked and nonranked data.	ITT, mITT
2	GSP change from baseline to EOT	Subjects with outlying data removed from analysis; using both ranked and non-ranked data (multiple	ITT, mITT

Version: 2.0 Page 33 of 74

		imputations for missing data).	
3	HDSM-Ax-7 2- point improvement from baseline to EOT	Missing data imputed as failure/non-response (single imputation only)	ITT, mITT
4	HDSM-Ax-7 2- point improvement and GSP change from baseline to EOT	Tipping point analysis (multiple imputations for missing data)	ITT, mITT
5	HDSM-Ax-7 2- point improvement from baseline to EOT	Analysis of the influence of the 7 individual items in the HDSM-Ax-7 scale (multiple imputations for missing data)	ITT, mITT

# 8.3.5.1 Sensitivity Analysis 1: GSP, All Available Data, no Imputations

To further investigate the robustness of the GSP co-primary efficacy endpoint, the ranked and non-rank-transformed GSP analyses will be repeated on all available data only without imputing missing data. The exact same analysis models (ANCOVA) will be used on the observed ranked and non-ranked change in GSP from baseline to EOT.

# 8.3.5.2 Sensitivity Analysis 2: GSP, Outlying Data Removed, Multiple Imputations

To further investigate the robustness of the GSP co-primary efficacy outcome, the ranked and non-rank-transformed GSP analyses will be repeated with outlier data (as defined in Section 8.2.1.2) removed from the analysis data set (both sofpironium bromide gel, 15% group and vehicle group) before any endpoint analysis is performed. The methodology will be similar to the primary analysis of the GSP co-primary endpoint. For missing data

Version: 2.0 Page 34 of 74

imputation purposes, outlier data will also be removed from the imputation sampling database. The exact same analysis models (ANCOVA) will be used on the observed ranked and non-ranked change in GSP from baseline to EOT. This differs from the analysis of the GSP co-primary endpoint, in that outlier GSP data is kept in the primary analysis but removed for this sensitivity analysis.

# 8.3.5.3 Sensitivity Analysis 3: HDSM-Ax-7, Missing Data imputed to Failure/Non-Response

In this analysis, missing EOT HDSM-Ax-7 cases will be analyzed as failure/non-responder in both treatment groups. The same co-primary HDSM-Ax-7 logistic regression model will be re-run on the HDSM-Ax dataset subjects with missing data modelled as not having improved by at least 2 points. The treatment success proportions estimates will also be reported.

# 8.3.5.4 Sensitivity Analysis 4: HDSM-Ax-7 and GSP, Tipping Point Analysis

A tipping point analysis will be conducted to investigate what type of missing data would cause a positive between-arm comparison of the outcomes of the co-primary efficacy endpoints to be non-significant. These analyses will be conducted separately for the HDSM-Ax-7 and GSP co-primary endpoints.

For the GSP co-primary endpoint, missing data in the vehicle arm will be assumed to be MAR, while missing data from the sofpironium bromide gel, 15% arm will be imputed assuming that subjects with missing data have missing GSP data that are worse by a prespecified  $\Delta$  compared to similar subjects with observed data. Missing values will be multiply imputed via this method with increasing  $\Delta$  values. A  $\Delta$  increment of 5 mg will be used for this study. The GSP co-primary efficacy outcome analysis methodology will be applied to the imputed datasets and repeated until statistical significance no longer holds. The tipping point at which the results are no longer significant will be identified and the results will be summarized graphically.

For the HDSM-Ax-7 co-primary endpoint, identical imputation methodology to that described above for the GSP will be applied to the HDSM-Ax-7 total scores, and the resulting values will be dichotomized into responders using the 2-point improvement criteria. A  $\Delta$  increment of 0.5 (in a 0-4 scale) will be used for this study. The HDSM-Ax-7 co-primary efficacy outcome analysis methodology will be applied to the imputed datasets and repeated until statistical significance no longer holds. The tipping point at which the results are no longer significant will be identified and the results will be summarized graphically.

Version: 2.0 Page 35 of 74

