#### 2 STUDY DESIGN

This is a multicenter, randomized, double-blinded, vehicle-controlled, Phase 3 study to evaluate the safety and efficacy of topically applied sofpironium bromide gel, 15% in subjects with primary axillary hyperhidrosis.

Approximately 350 subjects, at up to approximately 45 clinical sites in the US, will be enrolled to obtain approximately 300 evaluable subjects at the end of study.

Subjects will be randomized 1:1 to receive sofpironium bromide gel, 15% or vehicle gel (175 subjects dosed with 15% gel and 175 subjects dosed with vehicle gel). Subjects will apply the investigational product once daily at bedtime to their axillae for 42 consecutive days.

Patient-reported outcomes HDSM-Ax, Patient Global Impression of Severity (PGI-S), Patient Global Impression of Change (PGI-C; EOT only), and DLQI, as well as Investigator-reported GSP, will be recorded during the study at predefined time points. Vital signs and local tolerability assessments will be collected at Visits 4 through 9 and Visits 12 (EOT) and 13. Adverse events will be collected at each post-Screening visit. Blood and urine samples will be collected and analyzed at Screening and Visit 12/EOT for routine hematology, chemistry, and urinalysis parameters. Additionally, a urine pregnancy test (UPT) for females of child-bearing potential (FOCBP) will be collected and analyzed at Visits 1, 4, 8, and 12.

A total of 13 scheduled visits will take place over approximately 11 to 15 weeks, depending on when the Baseline Visit (treatment) is scheduled after the three (3) screening period visits: initial screening, GSP1, and GSP2. See Section 7.1 for an events table of this study.

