## 10.5 Sample Size

Sample size estimation was performed for the co-primary efficacy endpoints based on the results of a Phase 2b study (BBI-4000-CL-203):

- HDSM-Ax-7 responder analysis: 2-point improvement response rates of 29.8% and 53.7% were assumed for the vehicle and sofpironium bromide gel, 15% arms, respectively. The power is 0.95 with 116 subjects per arm and a total of 232 subjects.
- GSP: using rank-transformed GSP data for change from baseline to EOT, a difference of 16.6 in mean ranks between the vehicle and sofpironium bromide gel, 15% arms, with a pooled standard deviation of approximately 39.5, was used for this purpose. Normal approximation yielded a sample size estimate of 296 subjects for the study, 148 each arm, in order to achieve 0.95 power for the GSP co-primary endpoint.

A chi-square test for the HDSM-Ax-7 endpoint and a two-sample t-test for the GSP endpoint were used to estimate the above sample size and power for each endpoint. With approximately 300 evaluable subjects, the overall study power to demonstrate a statistically significant treatment effect (two-sided p < 0.05) for both coprimary efficacy endpoints simultaneously is greater than 0.90 (with greater than 0.95 power for each of HDSM-Ax-7 and GSP).

Assuming missing data from approximately 15% of subjects, a total of 350 subjects will be targeted for enrollment.

Additionally, sample size estimation was also performed using non-rank-transformed GSP data. An expected mean treatment difference of 73 mg with a pooled standard deviation of approximately 170 was used for this purpose. This yielded a reduced sample size estimate compared with the target of 300 subjects completing the coprimary efficacy assessments in order to achieve 0.95 power for GSP, further indicating that our sample size estimations are conservative.

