## 2.6 Sample Size Determination

Sample size estimation was performed for the co-primary efficacy endpoints based on the results of a Phase 2b study (BBI-4000-CL-203):

- HDSM-Ax-7 responder analysis: 2-point improvement response rates of 29.8% and 53.7% were assumed for the vehicle and sofpironium bromide gel, 15% arms, respectively. The power is 0.95 with 116 subject per arm and a total of 232 subjects.
- GSP: using rank-transformed GSP data for change from baseline to EOT, a
  difference of 16.6 in mean ranks between vehicle and sofpironium bromide gel,
  15% arms, with a pooled standard deviation of approximately 39.5, was used for
  this purpose. Normal approximation yielded a sample size estimate of 296
  subjects for the study, 148 in each arm, in order to achieve 0.95 power for the
  GSP co-primary endpoint.

A chi-square test for the HDSM-Ax-7 endpoint and a two-sample t-test for the GSP endpoint were used to estimate the above sample size and power for each endpoint. With approximately 300 evaluable subjects, the overall study power to demonstrate a statistically significant treatment effect (two-sided p < 0.05) for both co-primary

Version: 2.0 Page 12 of 74

endpoints simultaneously is greater than 0.90 (with greater than 0.95 power for each of HDSM-Ax-7 and GSP). It is estimated that 350 total subjects will need to be randomized (in a 1:1 allocation) for there to be 300 subjects completing the co-primary efficacy assessments (approximately 15% drop-out rate).

Additionally, sample size estimation was also performed using non-rank-transformed GSP data. An expected mean treatment difference of 73 mg with a pooled standard deviation of approximately 170 was used for this purpose. This yielded a reduced sample size estimate compared with the target of 300 subjects completing the co-primary efficacy assessments in order to achieve 0.95 power for GSP, further indicating that our sample size estimations are conservative.

Version: 2.0 Page 13 of 74

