## 8.3 Analysis Methods

With the exclusion of Section 8.3.7 Exploratory Efficacy Analyses, all other Section 8.3 analyses will be repeated for the mITT population.

The primary efficacy analysis will be performed on the ITT population with missing values imputed. The co-primary efficacy outcomes are:

- The proportion of subjects achieving at least a 2-point improvement in the HDSM-Ax-7 scale score from baseline to EOT in the sofpironium bromide gel, 15% group versus vehicle; and
- The change in GSP from baseline to EOT in the sofpironium bromide gel, 15% group versus vehicle.

Both comparisons will be conducted using two-sided tests at an alpha=0.05 level. Both endpoints will need to demonstrate a statistically significant positive result in favor of sofpironium bromide gel, 15% for the study to be considered successful.

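### The HDSM-Ax-7 tipping-point analysis shifts only the active arm, so its stopping rule is often never met and better-than-MAR vehicle dropouts go untested

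*SAP*

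**What the plan says.** SAP 8.3.5.4 sets out to find what missing data would turn a positive comparison non-significant, separately for each co-primary endpoint. Protocol 10.3.5 (Sensitivity Analysis 4) describes the same procedure.

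- **Vehicle arm:** "missing data in the vehicle arm will be assumed to be MAR". It is never shifted.
- **Active arm:** imputed values are made worse by delta, in steps of 5 mg for GSP and 0.5 on the 0-4 scale for HDSM-Ax-7.
- **HDSM-Ax-7:** the shift is applied to the total score, which is then split into responder or non-responder at a 2-point improvement.
- **Stopping rule:** the primary analysis method "will be applied to the imputed datasets and repeated until statistical significance no longer holds". The tipping point is then to be identified and shown graphically.

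Neither section states a maximum delta, what to report if significance is never lost, or any shift of the vehicle arm. The significance criterion comes from SAP 8.3: "Both comparisons will be conducted using two-sided tests at an alpha=0.05 level".

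**The concern.** Delta can do only so much to a yes/no endpoint. Once all missing active subjects are non-responders, further steps leave the data unchanged. If the comparison is still significant there, the rule as written has no end and the promised tipping point does not exist.

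The second issue is direction. The primary analysis already imputes missing active subjects from a vehicle-based model and holds vehicle at MAR (SAP 8.2.1.1). Sensitivity Analysis 3 fails missing subjects in both arms. No planned missing-data analysis makes vehicle dropouts do better than MAR. When worsening the active arm cannot overturn the result, that is the direction that still could, so the section's own question is only half answered. If the range or a vehicle shift has to be chosen after the results are known, the analysis also loses the benefit of being prespecified.

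**Working it through.** **Inputs**
- Response rates (SAP 2.6): "2-point improvement response rates of 29.8% and 53.7% were assumed for the vehicle and sofpironium bromide gel, 15% arms, respectively".
- Stated size (SAP 2.6): "The power is 0.95 with 116 subject per arm and a total of 232 subjects". Planning test: "A chi-square test for the HDSM-Ax-7 endpoint".
- Randomised (Protocol 2): "175 subjects dosed with 15% gel and 175 subjects dosed with vehicle gel".
- Missing data (Protocol 10.5): "Assuming missing data from approximately 15% of subjects, a total of 350 subjects will be targeted for enrollment".
- Twenty imputations combined by Rubin's rules (SAP 8.2.1.1).
- Assumed here: equal missingness in both arms, and planning rates that hold among observed subjects.

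**1. Reproduce the plan's figure.** With pbar = (0.537 + 0.298)/2 = 0.4175,

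n = [1.960 × √(2 × 0.4175 × 0.5825) + 1.645 × √(0.537 × 0.463 + 0.298 × 0.702)]² / 0.239² = 107.7, that is 108 per arm.

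The continuity correction, (n/4) × [1 + √(1 + 4/(0.239n))]², gives 115.9, that is 116 per arm. This matches the plan. Without the correction, power at 116 per arm is 0.963.

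**2. Where delta stops mattering.** Entry requires a baseline of 3 to 4 (Protocol 4.2), so a responder needs an end-of-treatment score of at most 2. If imputed scores stay within 0-4, any delta above 2 makes every missing active subject a non-responder. The first such step is 2.5, the fifth. In a simulation with untruncated scores (assumed SD 1.2), results stopped changing at about delta = 4.

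**3. The floor at 15% missing.**
- Active: 0.85 × 53.7% = 45.6%. Vehicle: 29.8%.
- Pooled rate 0.377; SE = √(2 × 0.377 × 0.623/175) = 0.0518.
- z = (0.456 − 0.298)/0.0518 = 3.06, p = 0.002. Whole counts of 80/175 against 52/175 also give p = 0.002.

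**4. How often the floor is still significant.** The analytic column is two-proportion power at 175 per arm. The simulated column uses 20 imputations and Rubin's rules on the log odds ratio; two values show the spread between runs.

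| Missing | Active rate at floor | Analytic | Simulated |
|---|---|---|---|
| 5% | 51.0% | 0.98 | 0.98 |
| 10% | 48.3% | 0.95 | 0.93 |
| 15% | 45.6% | 0.87 | 0.85 |
| 20% | 43.0% | 0.73 | 0.67 to 0.69 |
| 30% | 37.6% | 0.34 | 0.27 to 0.28 |

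At 15% missing, the range across methods is 0.83 to 0.88. These include a random number missing (0.833) and logistic regression with baseline, without and with 20 center terms (0.836 and 0.874). Among trials whose primary analysis is significant, the share is 0.872.

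**5. Compare Sensitivity Analysis 3.** With failures in both arms, vehicle becomes 0.85 × 29.8% = 25.3%. Then 45.6% against 25.3% gives z = 3.97, p about 0.00007. The tipping-point floor (z = 3.06) is clearly harsher.

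**6. The direction not varied.** Keep all missing active subjects as failures and let missing vehicle subjects respond at rate v. Vehicle rate = 0.85 × 29.8% + 0.15 × v.

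| v | Vehicle rate | z | p |
|---|---|---|---|
| 29.8% | 29.8% | 3.06 | 0.002 |
| 53.7% | 33.4% | 2.35 | 0.019 |
| 60% | 34.3% | 2.16 | 0.031 |
| 70% | 35.8% | 1.87 | 0.062 |
| 100% | 40.3% | 1.00 | 0.32 |

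These are expected-count calculations. Adding Rubin's between-imputation variance gives p = 0.037 at 60% and 0.068 at 70%, so the boundary stays between those two rates.

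**7. GSP.** On continuous GSP an unlimited mg shift will eventually remove significance. If normality fails and ranks are used (SAP 8.3.2), an imputed value cannot pass the top rank, so a similar ceiling can apply. Its size depends on the GSP distribution, which the documents do not give.

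**The case against.** The strongest reply is that a result which never tips answers the question: no departure in the active arm overturns it. That stands. Shifting one arm with control held at MAR is also a recognised conservative design, prespecified in both documents. The 0-4 scale implies a practical limit of eight 0.5 steps, so a programmer would not loop forever. On this view the gap is one missing sentence. That is fair for the end point and reporting rule. It does not meet the second half of the point, that no planned analysis varies vehicle dropouts upward.

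Two stronger readings are tempting and fail on the figures above. A reader might infer that the analysis merely repeats Sensitivity Analysis 3; it is stricter. A reader might also take the extreme corner, with all missing active subjects failing and all missing vehicle subjects responding (z = 1.00), as a sign of fragility. The boundary is far short of that corner but still at 60% or more, at least twice the assumed vehicle rate of 29.8%, and many would find that implausible.

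The imputation flow charts (SAP 18.2 and 18.3) could not be seen, and the table and figure specifications are in a separate document. A limit stated only there cannot be excluded.

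**Conclusion.** The point holds as a worthwhile, inexpensive improvement to a sensitivity analysis. At the plan's own rates with 15% missing, the HDSM-Ax-7 stopping rule is never met in about 85% of trials. That share is not a fixed property of the plan: it runs from about 98% at 5% missing to under 30% at 30% missing. It rests on equal missingness by arm and on the planning rates holding among observed subjects.

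A reader might infer that the primary result or the error control is in doubt. The documents do not support that, because neither the primary analysis nor the testing sequence depends on this section. Nor do they support a figure for ranked GSP. What remains is an analysis with no stated end or reporting rule, which leaves unmapped the direction in which the result could turn.

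**What to change.** In SAP 8.3.5.4, and in Protocol 10.3.5 if it is amended, replace the one-way loop with a two-way delta grid for each co-primary endpoint: active imputed values shifted worse, vehicle imputed values shifted better.

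- **HDSM-Ax-7:** 0.5 steps in each arm, with shifted scores kept within 0-4 and the grid ending at the scale bounds.
- **GSP:** mg steps up to a prespecified maximum shift, on whichever scale (continuous or ranked) the primary analysis uses.
- **Reporting:** give the estimate and p-value at every pair and mark the non-significance boundary. If there is none, state that no tipping point exists within the possible range.

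The present analysis remains visible as the edge of the grid with zero vehicle shift. The cost is SAP wording, more runs of existing code and a larger display. No new data are needed and the primary analysis is unchanged. The limits should be fixed before unblinding.

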# 8.3.5.5 Sensitivity Analysis 5: Analysis of the Influence of 7 individual items in the HDSM-Ax-7 scale

Sensitivity analyses will be conducted on the missing data imputed ITT Population to investigate whether any of the individual items in the HDSM-Ax-7 scale are overly influencing changes observed in the total score. First, a subject will be counted as a responder if they achieve at least a 2-point improvement in the individual question from baseline to EOT. The logistic regression model for the primary analysis for HDSM-Ax-7 will be repeated for each of the 7 individual items, and each individual question will be analyzed separately. Secondly, one of the 7 items will be omitted, and the HDSM-Ax-7 total score will be calculated as the average of the remaining 6 items. The primary logistic regression analysis for 2-point improvement response rate will be performed on this 6-item scale. This process will be repeated 7 times, each time with a different item of the HDSM-Ax-7 scale removed from calculation of the overall score.

## 8.3.6 Secondary Efficacy Analyses

The three secondary efficacy endpoints are described in Section 8.1.3.

If both co-primary analyses yield statistically significant results in favor of the sofpironium bromide gel, 15% group, the three secondary efficacy endpoints will be tested in the ITT population in a fixed sequence in the order presented in Section 8.1.3. Testing will continue only if all previously tested null hypotheses have been rejected at the 2-sided alpha < 0.05 significance level in favor of sofpironium bromide gel, 15%.

The analysis of the three responder secondary endpoints specified in Section 8.1.3 will be conducted using the same logistic regression model as that used for the HDSM-Ax-7 co-primary efficacy analysis. For each model, the covariates include treatment, baseline parameter score, and analysis center. For the composite endpoints, both HDSM-Ax-7 baseline and GSP baseline will be included as covariates.

## 8.3.7 Exploratory Efficacy Analyses

The exploratory efficacy endpoints are fully described in Section 8.1.4. All exploratory efficacy endpoints that involve a proportion of responders will be analyzed using methods similar to what was described for the HDSM-Ax-7 co-primary endpoint. For each endpoint, a logistic regression model will be generated using planned covariates of treatment, baseline parameter, and analysis center. For the composite endpoints, both baseline HDSM-Ax and GSP will be included as covariates.

All other exploratory endpoints that involve a change from baseline to a single timepoint for a continuous variable will be analyzed using methods similar to what is described for the GSP co-primary endpoint. For each endpoint, an ANCOVA model will be generated with fixed effects for treatment, baseline parameter, and analysis center.

Version: 2.0 Page 36 of 74

Change in PGI-S from baseline and PGI-C score (only collected at Day 43) will be analyzed using a Cochran-Mantel Haenszel (CMH) test for ordinal data to compare the treatment arms at each visit.

All exploratory efficacy analyses will be based on available data and missing GSP and HDSM-Ax EOT data imputed per Section 8.2.1. HDSM-Ax-11 will be calculated in the same manner as HDSM-Ax-7 at EOT, where the mean is derived from imputed sub-items for the EOT score. In addition, all continuous parameters will be summarized by visit on the ITT population.

Data in the analysis of rank-based GSP change from baseline to each timepoint will be ranked in the same manner as that of the co-primary GSP endpoints (Section 8.3.2).

Proportion of subjects achieving 1- and 2-point improvement from baseline in HDSM-Ax-7 and HDSM-Ax-11 will be plotted at each timepoint. Similar plots will be generated for proportion of subjects achieving 50% and 70% reduction in GSP from baseline at each timepoint and for the secondary composite endpoints. Plots will be generated for change from baseline for continuous measures over time.

In addition, a summary table of frequency of missing measurements at each visit will be generated for GSP and HDSM-Ax-7, separately.

All secondary and exploratory efficacy endpoints will be analyzed for both the ITT and PP populations. The co-primary endpoint primary analyses will also be analyzed for the PP population as an exploratory analysis. Analyses completed on the PP population will not be multiply imputed. The PP population is a completers population and analyses based on this population will use observed data. P-values for exploratory efficacy endpoints will be provided for descriptive purposes only and no formal hypothesis testing will occur.

